4.2 Secondary Endpoints

- Pre-post change in cognitive function
- Pre-post change in motor function

- Pre-post change in mood and apathy

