12.1 Statistical Analysis Overview

Due to the small sample size of this study, statistical analysis will be mainly exploratory and descriptive: t-tests (or Mann-Whitney u-tests if normality of the data is not met) are used to compare the difference of a continuous measure between groups (such as patient age at baseline, various efficacy measures), and contingency tables and chi-square tests are used to compare the difference of a categorical variable (such as patient gender at baseline, various safety and adverse events).

To minimize the potential confounding effects of gender and MOCA score on the treatment effect, we will use stratified block randomization when assigning patient to one of the four study groups. The stratification factors will be gender (male/female) and MOCA score (low <22/30 and high>23/30). We will use block size of four.

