12.2 Statistical Analysis of Primary Aim – safety, tolerability and adverse events

To assess safety and tolerability of the study drug at varying dose levels, AEs and SAEs will be categorized and summarized by study group. We will descriptively note if any group was more likely to have experienced a particular AE/SAE or generally experienced more AEs/SAEs throughout the course of the study; if we notice a significant ‘spike’ associated with a particular dosing group for a certain event, we’ll construct a chi-square test to see if it’s statistically significant. We will also assess the number of and reason for early withdrawals in each study group.

We will also monitor two key safety measures: 1) a fasting glucose < 70 mg/dL and 2) an unintended weight loss of >5% (relative to the patient’s weight at visit 2). The number of participants in each group who experience either or both of these events will be counted and descriptively compared. We will then compare the change in fasting glucose and weight at Visit 2 (Baseline/Initial Treatment) and Visit 3 (Final Treatment/Safety). In the event of an early withdrawal, measures taken at the early withdrawal visit will be used in place of Visit 3 data. We will descriptively note if any dosing group was more inclined to experience one or both of these safety events. In a similar fashion, if we notice a significant ‘spike’ associated with a particular dosing group, we’ll construct a chi-square test to see if it is statistically significant.

Secondarily, we will report the incidence of mild, moderate, and severe hypoglycemia overall and by group. Mild hypoglycemia will be defined as $54 \text{ mg/dL} \leq \text{fasting glucose} < 70 \text{ mg/dL}$; moderate hypoglycemia is $40 \text{ mg/dL} \leq \text{fasting glucose} < 54 \text{ mg/dL}$; and severe hypoglycemia is $\text{fasting glucose} < 40 \text{ mg/dL}$.

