12.3 Statistical Analysis of Second Aim – efficacy measures

For each of the efficacy outcome measures, we will report mean differences and 95% confidence intervals between Visit 2 (Baseline/Initial Treatment) and Visit 3 (Final Treatment/Safety) for each study group. In the event of an early withdrawal, measures taken at the early withdrawal visit will be used in

place of Visit 3 data, if possible. Possible trends in cognitive function, motor function, and mood and apathy scores will be addressed.

We will look at the individual components and domains assessed by the chosen cognitive, motor, mood, and apathy measures to determine if any appear to be more sensitive to IN insulin. We will also explore the data for components that have a larger dose response. That is, they increase or decrease as the dose-level increases.

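### Randomisation is stratified by gender and MoCA, but the named group comparisons adjust for neither these nor the Visit 2 score; one four-arm model would be a cheap, modest gain in precision

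*Combined protocol and SAP*

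**What the plan says.** Section 12.1 gives the reason for stratifying: "To minimize the potential confounding effects of gender and MOCA score on the treatment effect, we will use stratified block randomization". It then defines the strata ("The stratification factors will be gender (male/female) and MOCA score (low <22/30 and high>23/30") and adds "We will use block size of four".

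For analysis, the same section says "t-tests (or Mann-Whitney u-tests if normality of the data is not met) are used to compare the difference of a continuous measure between groups", with efficacy measures among its examples, and "contingency tables and chi-square tests are used to compare the difference of a categorical variable". No section names a regression model, ANCOVA, a stratified test or any covariate.

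For efficacy, section 12.3 says "we will report mean differences and 95% confidence intervals between Visit 2 (Baseline/Initial Treatment) and Visit 3 (Final Treatment/Safety) for each study group". That is an interval within each arm; no between-group interval is specified. The secondary endpoints are changes (section 4.2: "Pre-post change in cognitive function"). For the safety measures section 12.2 also works with change: "We will then compare the change in fasting glucose and weight at Visit 2 (Baseline/Initial Treatment) and Visit 3 (Final Treatment/Safety". The Visit 2 value therefore enters the analysis by subtraction.

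Sections 12.1 and 12.4 describe the analysis as mainly exploratory and descriptive, and section 12.4 considers no power. Planned arm sizes (Table 2) are 7, 7, 9 and 7 for 20 IU, 40 IU, 80 IU and placebo.

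**The concern.** The design treats gender and MoCA as factors that could matter for the outcome, and the analysis then leaves them out. If they do predict the quantity analysed, stratification makes the arms more alike on them, which lowers the true variance of the treatment contrast. An unadjusted standard error still contains their variance. The interval is then wider than it need be and the test is conservative.

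Two other sources of precision are also left unused. A change score subtracts the whole Visit 2 value, where ANCOVA subtracts only the part that predicts Visit 3. A two-sample test estimates the variance from 14 to 16 participants, where a four-arm model uses all 30.

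Section 12.4 wants a safe dose with trends in the secondary outcomes, and section 12.3 looks for sensitive measures and a dose response. With 7 to 9 per arm, both depend on precision.

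**Working it through.** **Inputs from the documents.** Arms of 7, 7, 9 and 7 (sum 30); change from Visit 2 as the endpoint; t-test between groups. The plan states no power, SD or effect size, so it has no figure to reproduce.

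**Assumptions.** SD = 1 at each visit, so results are in SD units; Visit 2–Visit 3 correlation ρ from 0.5 to 0.9; two-sided 5% tests.

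**Step 1: closed form, 80 IU (n=9) against placebo (n=7), gender and MoCA not predicting change.**

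Half-width = t(0.975, df) × SD factor × √(1/7+1/9) × penalty, with √(1/7+1/9) = 0.504. The SD factor is √(2(1−ρ)) for change and √(1−ρ²) for ANCOVA. The penalty for q covariates is √(1+q/(df−1)), where df is the residual df after adjustment.

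At ρ = 0.5:
- t-test on change, 14 df: 2.145 × 1 × 0.504 = 1.08.
- Change with variance pooled over four arms, 26 df: 2.056 × 1 × 0.504 = 1.04.
- Four-arm ANCOVA with three covariates, 23 df: 2.069 × 0.866 × 0.504 × √(1+3/22) = 0.96.
- The same three covariates in the two arms alone, 11 df: 2.201 × 0.866 × 0.504 × √(1+3/10) = 1.10.

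| ρ | t-test on change | Change, pooled variance | Four-arm ANCOVA, Visit 2 only | Four-arm ANCOVA, three covariates | Narrower than t-test | Two-arm ANCOVA, three covariates |
|---|---|---|---|---|---|---|
| 0.5 | 1.08 | 1.04 | 0.92 | 0.96 | 11% | 1.10 |
| 0.7 | 0.84 | 0.80 | 0.76 | 0.79 | 5% | 0.90 |
| 0.8 | 0.68 | 0.66 | 0.64 | 0.67 | 2% | 0.76 |
| 0.9 | 0.48 | 0.46 | 0.46 | 0.48 | 0% | 0.55 |

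In this setting the gain comes from pooling (about 4%) and from ANCOVA in place of a change score. The two stratum terms cost a little (0.92 to 0.96 at ρ = 0.5). Inside a two-arm subset the covariates widen the interval by 1% to 14%. There, gender and MoCA would have to explain about 18% of residual variance (22% for 7 against 7) to repay their degrees of freedom.

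**Step 2: simulation with stratified blocks.** 30 participants, one participant per arm in each block of four, four strata, at least 3,000 trials per setting. Further assumptions not in the documents: 60% male and 35% with low MoCA.

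- *Factors shift neither visit, or both visits equally.* The interval is about 14%, 8%, 6% and 3% narrower at ρ = 0.5, 0.7, 0.8 and 0.9, and the t-test's size is about 5%. An equal shift at both visits cancels in the change score. With a fixed 7:7:9:7 split the gains are about 11%, 5% and −1% at ρ = 0.5, 0.7 and 0.9, in line with step 1.
- *Each factor shifts Visit 3 by 0.3–0.7 SD beyond Visit 2.* The interval is 11–27% narrower at ρ = 0.5 to 0.8. At 0.7 SD the t-test's size is 3.4% and 2.4% at ρ = 0.5 and 0.7, and a little under 2% at 0.8; ANCOVA stays near 5%. Power for a true 1 SD difference, at ρ = 0.5–0.7, rises from 36–61% to 53–71%.

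The block results are somewhat larger than the fixed-split ones. Stratified blocks nearly balance gender and MoCA, so less of the covariate penalty is paid, and the arm sizes differ from 7:7:9:7.

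**The case against.** The strongest reply is that little is at stake. The trial's primary aim is safety, it is declared exploratory and unpowered, and section 12.3 promises only within-arm intervals and possible trends. Stratification does its stated job at allocation, so leaving the factors out of the analysis does not bias the comparison. That stands and limits the weight of the point.

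A reader might infer that the plan ignores the Visit 2 score. It does not: the endpoints are changes from Visit 2. The gap is only that change is not further adjusted for it.

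A reader might also infer that precision gained by stratifying is certainly lost and that the planned tests are certainly conservative. The documents do not support this. Both need gender and MoCA to predict three-week change, or raw Visit 3 scores to be compared. Nothing in the documents speaks to the first, and section 4.2 points to change scores.

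A further fair point is that section 12.1 has a rank-test fallback for non-normal data, which a single linear model for every score would drop. Several scores are timed or bounded, so a fallback has to stay. Rare safety events in arms of 7 to 9 could not usefully carry covariates, and the point does not extend to them.

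**Conclusion.** The point holds as an improvement and does not show an error that invalidates a result. The named between-group comparisons adjust for neither the stratification factors nor the Visit 2 score, and one four-arm model would usually give narrower intervals from data already collected.

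For 80 IU against placebo the gain is about 14% to 3% at correlations 0.5 to 0.9 when the factors do not predict change, or about 11% to none with a fixed 7:7:9:7 split. It is about 11–27% at correlations 0.5–0.8 when each factor moves Visit 3 by 0.3–0.7 SD beyond Visit 2; only then is the t-test conservative. The correlation, the stratum effects and the stratum shares are all assumed. The gain should not be credited to the strata alone, since part comes from pooling the variance and part from replacing the change score.

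The impact is modest in an exploratory trial that is mainly about safety.

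**What to change.** In sections 12.1 and 12.3, before unblinding, specify for each efficacy score one linear model on all randomised participants with data: Visit 3 score on dose group (four levels), Visit 2 score, gender and screening MoCA.

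- Enter screening MoCA as a continuous covariate. This also avoids the gap in the strata as written, where scores of 22 and 23 belong to neither group.
- For the MoCA outcome, use screening MoCA as the baseline, because Table 3 schedules MoCA at screening and Visit 3 only.
- Report adjusted between-group differences with 95% intervals. Keep raw arm means and SDs as description.
- Keep a fallback, such as a transformation or rank-based ANCOVA, for clearly non-normal scores.
- Do not fit these covariates within two-arm subsets of 14 to 16 participants.

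The cost is SAP wording and one model per score, with no change to any participant procedure. The statistical price is three covariate degrees of freedom (23 residual df instead of 26) and a common-variance assumption, which the arm SDs let the reader judge.

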
Primary Objectives:
 
 • To determine the safety and tolerability of three different doses of intranasal insulin in patients with Parkinson's disease (PD) 	

Secondary Objectives:
 
 • To evaluate efficacy of intranasal insulin on cognitive functioning in PD • To evaluate efficacy of intranasal insulin on motor function in PD • To evaluate efficacy of intranasal insulin on mood and apathy in PD • To identify which outcome measures are most sensitive to effects of intranasal insulin in PD 	
STUDY DESIGN	
Study Type	Dose-finding
Control Type	None
Study Indication Type	Dose-finding, safety
Blinding Schema	Double blinded
Device	SipNose nasal device
Study Design	randomized, parallel-group, double blind, placebo-controlled
Planned Duration of Subject Participation	8 weeks (Treatment duration: 3 weeks)
PRIMARY ENDPOINTS	

 • Composite safety event of either: a reduction of fasting glucose to <70 mg/dL or an unintended reduction of weight >5% • Pre-post change in safety measures (fasting glucose and weight) • Number of AEs and SAEs 	
SECONDARY ENDPOINTS	

 • Pre-post change in cognitive function measures 	

 • Pre-post change in motor function measures • Pre-post change in mood and apathy measures 	
INVESTIGATIONAL PRODUCTS, DOSE AND MODE OF ADMINISTRATION	
Investigational Product	
Regular insulin (Novolin-R) in 3 different doses and placebo
 
Dose 1, group with 7 participants: 20 IU/IN (10 units IN in one nostril twice daily x 21 days, volume 100 µl)
 
Dose 2, group with 7 participants : 40 IU/IN (10 units IN in each nostril twice daily x 21 days, volume 100 µl)
 
Dose 3, group with 9 participants: 80 IU/IN (20 units IN in each nostril twice daily x 21 days, volume 200 µl)
 
Dose 4, group with 7 participants: placebo (each nostril, twice daily)

SUBJECT SELECTION	
Targeted Accrual	30 subjects. We estimate a need to consent 50 participants in order to reach this goal.
INCLUSION CRITERIA	

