
 1. Subject has Idiopathic PD defined by the cardinal sign, bradykinesia, plus the presence of at least 1 of the following: resting tremor or rigidity and without any other known or suspected cause of Parkinsonism (according to MDS clinical diagnostic criteria for Parkinson's disease- Postuma et al, Movement Disorders 2015), confirmed by a fellowship trained movements disorder specialist 2. Subject is Hoehn & Yahr stage less than or equal to 3 3. Subject has a MOCA score ≥16. 4. Subject is > 40 and <90 years of age. 5. Female subjects are post-menopausal or have a negative pregnancy test 6. The subject must be proficient in speaking, reading and understanding English in order to comply with procedural testing of cognitive function, memory and physiology. 7. Subject has provided informed written consent prior to participation. In the event that subject is legally unable to provide informed written consent due to deterioration in cognitive abilities, fully informed written consent must be provided by a legally authorized representative. 8. Subject is on a stable dose (at least 1 month prior to baseline visit) of antiparkinsonian agents and is willing to remain on this dose for the duration of the study. If the subject is on a cholinesterase inhibitor, a stable dose without changes for 1 month is also required. 9. Subject has undergone a brain CT or MRI prior to the study as part of their previous diagnostic workup for PD to rule out underlying structural lesions, as determined clinically significant by the investigator 	

EXCLUSION CRITERIA

1. Subject has atypical Parkinson's syndrome(s) due to drugs (e.g., metoclopramide, neuroleptics), metabolic neurogenetic disorders (e.g., Wilson's Disease), encephalitis, cerebrovascular disease, or degenerative disease (e.g., Progressive Supranuclear Palsy, Multiple System Atrophy, Corticobasal Degeneration, Lewy Body dementia)
2. Subject has medical history and/or clinically determined disorders: chronic sinusitis, untreated thyroid disease, or significant head trauma.

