4.3 Safety

- Incidence and severity of serious adverse events (SAEs) and adverse events (AEs)
- Frequency of change in clinically-significant vital signs, physical exam or neurological exam
- Plasma glucose level <70mg/dl
- Change in weight

5 Study Design

This study is a single center trial to determine dose finding, safety and tolerability of 3 doses of intranasal (IN) regular insulin (Table #2) and placebo in patients with Parkinson's disease.

Table 2: Intranasal Drug Dosing

Group	Drug	Dose	Volume	N=
Dose group 1	Insulin	20 IU/IN (10 IU, one nostril, twice daily)	100µl	7
Dose Group 2	Insulin	40 IU/IN (10 IU, each nostril, twice daily)	100µl	7
Dose Group 3	Insulin	80 IU/IN (20 IU, each nostril, twice daily)	200µl	9
Dose Group 4	Placebo	0.9% Saline (each nostril, twice daily)	200µl	7

After written informed consent has been obtained from the subject and family member/caregiver, subjects will be screened to assess study eligibility based on study inclusion/exclusion criteria. Subjects who are eligible at the end of the screening visit (Visit 1) will be scheduled for a baseline and randomization visit (Visit 2). During the baseline visit, subjects will be administered a cognitive battery. Subjects will also undergo a neurological examination, including the UPDRS (United Parkinson's Disease Rating Scale- MDS) to be performed in the "ON-STATE" (after taking Anti-Parkinson's medications according to the subject's regular medication schedule). A final safety/assessment visit will take place 3 weeks after visit 2 at which time the tests will be re-administered.

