7.5 Neuropsychological Assessment

The neuropsychological battery consists of subtests in a variety of domains that include working memory, visuospatial skills, processing speed, inhibition, set-shifting, verbal fluency, learning, memory, and mood.

7.5.1 Global Cognition:

7.5.1.1 *Montreal Cognitive Assessment*

The Montreal Cognitive Assessment (MoCA) is a brief cognitive screening measure that has been validated for use among individuals with Parkinson's disease. The total score for this test is 30 points, but one point will be added for individuals with ≤ 12 years of education, up to a maximum of 30 points. The cutoff point for normal cognition is 26/30 in the general population (Nasreddine et al., 2005) and in individuals with Parkinson's Disease (Hoops et al., 2009).

7.5.2 Working Memory:

7.5.2.1 *WAIS-IV Digit Span:*

The Digit Span task includes three different components: Digits Forward, Digits Backward, and Digit Sequencing (Wechsler, 2008). During Digits Forward, the participant is read a series of numbers and is asked to recall the numbers in the same order. Digits Backward requires the participant to recall the numbers in reverse order. Digit Sequencing requires the participant to recall the numbers in ascending order. During the first trial of each component, only 2 digits are read to the participant and the number of digits become gradually longer in length as the test continues.

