10.2 Subject Withdrawal

Subject may withdraw from study at any time for any reason without penalty or be terminated from the study by the clinical investigator (see provisions for termination by study team.) Investigational team will document the reason(s) for withdrawal. In the event a subject chooses to withdraw from study before Visit 3, the safety procedures described in Section 7.3 will be performed ideally within 3 days following subject's decision to withdraw. For all subjects who withdraw, all final safety assessments will be collected regardless of time elapsed since previous visit. In addition to the termination visit, subjects who withdraw early will be contacted within 7 days by study staff via telephone to assess development

of new and/or ongoing AEs and concomitant medications. Efforts will be made to recruit subjects to replace any withdrawals before randomization so as to maintain an n=30.

Subject's participation may be terminated at the discretion of the investigator. Individuals may be withdrawn for the following reasons:

- Clinically significant adverse events
- Lost to follow-up
- Protocol violations
- Inability to tolerate study medication
- Other

11 Adverse Events (AE) and Serious Adverse Events (SAE)

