12.4 Statistical Power

As stated above, due to the sample size limitation of this study, no particular statistical power is under consideration during the study design phase with the intent to detect a meaningful clinically significant difference between study groups for any of the primary or secondary outcome measures; statistical analysis of this study will be mainly exploratory and descriptive.

The overall goal of the study is to identify a safe dose intranasal insulin with trends towards the secondary outcomes. Three different doses (and placebo) will be used, with the highest number of subjects (9) in the group with the highest dose, a model previously used by Finger et al. (2014).

13 Study Conduct Considerations

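### The randomisation rule in 12.1 leaves MoCA 22 and 23 without a stratum, and its blocks of four do not aim at the planned 7/7/9/7 groups

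*Combined protocol and SAP*

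**What the plan says.** Section 12.1 gives the only allocation rule in the document. Its purpose is stated first: "To minimize the potential confounding effects of gender and MOCA score on the treatment effect, we will use stratified block randomization". The detail follows: "The stratification factors will be gender (male/female) and MOCA score (low <22/30 and high>23/30). We will use block size of four". No allocation ratio is given.

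The passages it has to fit are these:

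- **Eligibility** (Protocol Summary and 6.1.1): "Subject has a MOCA score ≥16". Neither list of criteria excludes 22 or 23.
- **MoCA scoring** (7.5.1.1): "The total score for this test is 30 points, but one point will be added for individuals with" at most 12 years of education, capped at 30.
- **Group sizes** (Protocol Summary, and Table 2 in section 5): seven at each of the two lower doses, seven on placebo, and "Dose 3, group with 9 participants: 80 IU/IN".
- **Intent** (12.4): "Three different doses (and placebo) will be used, with the highest number of subjects (9) in the group with the highest dose", following an earlier dose-finding trial.
- **Total** (10.2): "Efforts will be made to recruit subjects to replace any withdrawals before randomization so as to maintain an n=30".

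**The concern.** There are two separate faults.

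**MoCA strata.** The low stratum stops below 22 and the high stratum starts above 23. An eligible patient who scores 22 or 23 has no list from which to be assigned. The likely cause is a slip with the inequality signs, but the repair is not unique. Cutting at ≤22 versus ≥23, at <22 versus ≥22, or at ≤23 versus >23 places these patients differently, and nothing in the document chooses among them.

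**Block size against group sizes.** Blocks of four over four arms lead to equal groups. The planned groups are unequal on purpose. The rule that would produce the extra top-dose places is not written down.

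What is at stake is a randomisation that can be carried out as written, and the balance on MoCA that 12.1 wants from stratifying. Cognitive change is a secondary endpoint, so that balance matters to the trial's own aims. If the plan is not settled in advance, someone has to decide case by case where a score of 22 or 23 goes and how the top-dose group is enlarged.

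**Working it through.** **1. Total.** 7 + 7 + 9 + 7 = 30, which agrees with the target accrual and with 10.2.

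**2. MoCA coverage.** Scores are taken as whole points, which is an inference from the 30-point scale and the one-point adjustment.

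- Eligible scores 16 to 30: 30 − 16 + 1 = 15 values.
- Low (<22), 16 to 21: 6 values.
- High (>23), 24 to 30: 7 values.
- Unassigned: 15 − 6 − 7 = 2 values, namely 22 and 23.

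The documents give no score distribution, so the number of patients affected is unknown. For illustration, if a share p of patients scores 22 or 23, the expected number is 30p and the chance of at least one is 1 − (1 − p)^30:

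| Assumed p | Expected of 30 | Chance of at least one |
|---|---|---|
| 5% | 1.5 | 79% |
| 10% | 3.0 | 96% |
| 25% | 7.5 | >99.9% |

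A wider assumption (roughly normal scores limited to 16–30, mean 22 to 28, SD 2 to 4) gives 0.4 to 11.5 of 30.

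**3. What blocks of four can deliver.** The only block of four that contains all four arms is 1:1:1:1. The expected size is therefore 30/4 = 7.5 in every arm. If all 30 patients fell in one stratum, the result would be seven full blocks and two more places: two arms of 8 and two of 7, never a 9. The ratio 7:7:9:7 has no common divisor, so the smallest single block that holds it exactly has 30 places.

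**4. How often 7/7/9/7 arises anyway.** It can occur only by chance, through incomplete blocks in different strata. Over every possible split of 30 across four strata, the highest probability is 6.25%. An example is a split of 29 and 1: seven full blocks, then one leftover patient in each of two strata, both of whom must draw the top dose, so 1/4 × 1/4 = 1/16.

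Averaging over plausible splits needs an assumed stratum mix. The simulation used 100,000 trials per mix, N = 30, four strata, and these male share/high-MoCA share mixes: equal strata, 60/50, 65/70, 60/80 and 70/85. The results barely depend on the mix:

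| Printed scheme | Result |
|---|---|
| Mean top-dose size | 7.50 |
| Exactly 7/7/9/7 | 2.8–3.1% |
| Nine or more at top dose | 9.0–9.1% |
| Top dose strictly the largest group | 8.6–8.7% |

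**5. An unwritten rule that would fit.** Seven full blocks (28 patients, 7 per arm) plus two extra top-dose places also makes 7/7/9/7. With four strata, seven blocks would be complete among 30 patients in only 14.5–18.1% of trials (400,000 draws per mix).

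**6. Effect on precision.** With zero events in n patients, the one-sided 95% upper bound on the event rate is 1 − 0.05^(1/n): 28% at n = 9, 31% at n = 8 and 35% at n = 7.

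**The case against.** The strongest reply is that little depends on this. The analyses in 12.2 and 12.3 are by study group and none uses the strata. Section 12.4 claims no power, and the work is described as exploratory. The zero-event bound moves by only a few points between seven and nine patients. All of that stands, and it limits the seriousness of the point.

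A second reply is that the MoCA gap may be an equality bar lost when the file was converted, so that the source reads ≤22 and ≥23. This cannot be excluded from the text. It is unlikely, because the same text keeps its ≥ and ≤ signs in the inclusion criteria, in 7.5.1.1 and in the hypoglycaemia definitions of 12.2.

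A third reply is that 12.1 omits the ratio rather than contradicting the group sizes, and that seven blocks with two added places would reconcile them. It is true that 7.5 per arm comes from reading the block size together with the number of arms. But no other block of four includes every arm, so the reading is hard to avoid, and the top-up rule appears nowhere.

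**Conclusion.** Both parts hold. Scores 22 and 23 have no stratum as printed, and the stated scheme targets 7.5 per arm, not the 7/7/9/7 that the protocol gives in two places and presents as deliberate in 12.4. The planned sizes are not impossible under the rule, but they would be a chance result: about 3% of trials under the assumed stratum mixes, and at most 6.25% for any split across strata.

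No planned estimate or test changes. The defect is that the list cannot be built from 12.1 without decisions the plan does not record. It should be fixed, but it is not a threat to the trial's conclusions. The conclusion rests on whole-point MoCA scoring and on each block containing every arm. The number of patients at 22 or 23 is unknown.

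**What to change.** Before the first randomisation, make two changes.

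1. **Give one MoCA cut without a gap.** For example, ≤22 versus ≥23 keeps both printed numbers. The sponsor should confirm which cut was intended.
2. **State the allocation ratio in 12.1 and make it agree with the group sizes.** There are two options:
   - **Option A, equal allocation.** Keep blocks of four and restate the groups as 1:1:1:1, about seven to eight each, in the Protocol Summary, Table 2 and 12.4. The cost is giving up the deliberately larger top-dose group.
   - **Option B, keep 7/7/9/7 as a target.** Use a concealed scheme that aims at it. One is mixed blocks: in each stratum list, five blocks of 1:1:1:1 and two of 1:1:2:1 in random order. That makes 5×4 + 2×5 = 30 places, with 5 + 2 = 7 in each of three arms and 5 + 2×2 = 9 at the top dose. Another is minimisation with a random element and the same target ratios. The block-size sentence in 12.1 must then be replaced.

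Under Option B the sizes should be called targets, because 30 patients spread over four strata leave the lists unfilled. With mixed blocks, simulation over the same mixes gives a mean top-dose size of about 9.0, 8 to 10 in 83–86% of trials, nine or more in 65–67%, and exactly 7/7/9/7 in 11–12%.

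The cost is one corrected cut point, one sentence on the ratio, the matching edits and a list generated to fit. Neither option needs extra participants or changes the planned analyses.
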